- 3.1.9 Total bilirubin must be < 1.5 x the upper limit of normal, unless the elevation of bilirubin is thought to be secondary to Gilbert's syndrome or cART. If, however, the elevated bilirubin is felt to be secondary to antiretroviral therapy, the total bilirubin must be $\leq 3.5 \text{ mg/dL}$, provided that the direct bilirubin is normal and the AST and ALT $\leq 3 x$ the upper limit of normal. Also, if the elevated bilirubin is thought to be secondary to cHL the same criteria for hyperbilirubinemia should be applied; however 1 prior cycle of cyclophosphamide is permitted in attempt to make the participant eligible (see Section 3.1.5). Patients should not be excluded from study participation unless dosing cannot be safely established as per Section 5.2.5.
- 3.1.10 Female participants must have a negative pregnancy test within 1 week of enrollment and **all** participants must agree to **use two reliable methods of contraception simultaneously** if conception is possible during the study and for 6 months after stopping treatment. Should a woman participant become pregnant or suspect she is pregnant while the participant is participating in this study, she should inform her treating physician immediately. The participant will then be removed from protocol therapy. Participants who father a child while participating in the study will be permitted to continue with the protocol. The participant, however, is required to notify the investigator if he fathers a child.
- _____ 3.1.11 Ability to understand and the willingness to sign a written informed consent document.
- 3.1.12 Karnofsky performance status > 30% (given the aggressiveness of this disease and the often severely debilitated nature of the patients at initial presentation). See Appendix III.
- 3.1.13 Measurable or non-measurable (evaluable) tumor parameter(s). Non-measurable tumor parameters will be defined as not having bi-dimensional measurements (i.e., gastric or marrow involvement) but can be followed for response by other diagnostic tests such as gallium, PET imaging and/or bone marrow biopsy.
- _____ 3.1.14 Patients already receiving erythropoietin or GCSF for treatment of HIV-related cytopenia are eligible.
- 3.1.15 CD4 count \geq 50 cells/µL.

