5.2 AVD-Brentuximab Vedotin Dose Modifications (applies to all cycles)

5.2.1 Hematologic Toxicity

Although it is common practice to attenuate doses or delay treatment due to cytopenias alone, recent studies have shown that in the non-HIV setting for cHL patients receiving delays results in suboptimal treatment outcomes^{77,78}. Participants will receive full doses of AVD on schedule on Days 1 and 15 of each 28-day cycle without treatment delays, unless neutropenic fever or documented infections are present.

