5.2.5 Impaired Hepatic Function

Table 5-C.

Please see Table 5-C below for the appropriate dose adjustments based on total bilirubin and AST. In cases of obstruction of the biliary duct by a tumor mass, a biliary drainage stent may be placed prior to chemotherapy. Values must be within protocol eligibility at treatment initiation.

Table 5-C:Total Bilirubin with Appropriate DoDose Adjustments		Doxorubicin and	d Vinblastii	ıe		
	Drug ¹	Total Bilirubin:	Total Bilirubin:	Total Bilirubin:	Total	

Drug ¹	Total Bilirubin:	Total Bilirubin:	Total Bilirubin:	Total
	< 1.5	1.5 – 3	3.1 – 3.5	Bilirubin:
	AST: < 60	AST: 60 - 180	AST: > 180	> 3.5
Doxorubicin	Administer	Administer	Administer	Safety Not
	100%	50%	25%	Established
Vinblastine	Administer	Administer	Administer	Safety Not
	100%	50%	25%	Established

If participants are receiving atazanavir, please use only the direct bilirubin as an indicator 1. for dose reduction of doxorubicin or vinblastine, following the dose reduction guidance identically as for total bilirubin

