- 8.1.6 MRI of the brain with and without IV gadolinium contrast, to look for early evidence of PML.
- 8.1.7 Determination of LVEF by MUGA scan or echocardiogram.
- 8.1.8 Bone marrow biopsy for histology and determination of percent bone marrow involvement. If bone marrow involvement by lymphoma has already been

documented after bone marrow biopsy performed more than 6 weeks prior to registration, the biopsy does not have to be repeated.

8.1.9 Central pathology review for confirmation of histology of lymphoma specimen: Biopsy material at diagnosis will be sent to confirm HIV-HL and histologic subtype. When possible, biopsy tissue blocks should be sent. If not, one hematoxylin and eosin (H&E) stained slide and ten 5 μ m blank (unstained) paraffin sections can be used instead. The tissue block will be returned to the sites. (See Appendix VIII for the acceptable specimens required for central review and for handling instructions).

All specimens will be reviewed by a panel of pathologists and must be submitted within 30 days of study enrollment. Participants who are found not to have HIV-HL will be withdrawn from the study

- 8.1.10 Three 1.0 mm cores from the initial biopsy tissue block will be required to be sent for miRNA analysis. If biopsy block is unavailable, 10 unstained sections at 20 microns can be submitted (See Appendix VIII for the acceptable specimens required for miRNA analysis and for handling and shipping instructions).
- 8.1.11 Three 1.0 mm cores from the initial biopsy tissue block will be required to be sent for tissue microarray analysis. (See Appendix VIII for the acceptable specimens required for TMA construction and analysis and for handling and shipping instructions).
- 8.1.12 Laboratory tests, including:
 - 8.1.12.1 CBC with differential and sedimentation rate (within 2 weeks prior to participant registration). Sedimentation rate is only required at screening/baseline.
 - 8.1.12.2 Serum chemistries: electrolytes (Na, K, Cl, bicarbonate, Ca, Mg, and phosphorus), glucose, blood urea nitrogen (BUN), creatinine, total bilirubin, alkaline phosphatase (ALP), LDH, total protein, albumin, AST and ALT (within 2 weeks prior to participant registration).
 - 8.1.12.3 CD4 and CD8 cell count.

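### The bilirubin rules for entry conflict when lymphoma raises direct bilirubin, and AMC Table 5-C may cut doxorubicin and vinblastine in Gilbert's participants who would get full dose in France

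*Combined protocol and SAP*

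**What the plan says.** **AMC protocol, 3.1.9 (entry).** Total bilirubin must be below 1.5 x ULN unless the rise is attributed to Gilbert's syndrome or antiretrovirals. For antiretrovirals the limit is total at most 3.5 mg/dL, direct normal, and AST and ALT at most 3 x ULN. Gilbert's has no stated ceiling. The next sentence covers lymphoma: "if the elevated bilirubin is thought to be secondary to cHL the same criteria for hyperbilirubinemia should be applied", and "1 prior cycle of cyclophosphamide is permitted in attempt to make the participant eligible". The item closes: "Patients should not be excluded from study participation unless dosing cannot be safely established as per" Section 5.2.5.

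**AMC protocol, 5.2.5 and Table 5-C (dose).** Doxorubicin and vinblastine are dosed on total bilirubin and AST:
- 100% for total below 1.5 with AST below 60;
- 50% for total 1.5 to 3 with AST 60 to 180;
- 25% for total 3.1 to 3.5 with AST above 180;
- no safe dose for total above 3.5.

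After a sentence on biliary stenting the text adds: "Values must be within protocol eligibility at treatment initiation". The only switch to direct bilirubin is the footnote "If participants are receiving atazanavir, please use only the direct bilirubin as an indicator", with the instruction to apply it "following the dose reduction guidance identically as for total bilirubin". By its heading, Section 5.2 covers every cycle, so cycle 1 is included.

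**French protocol.** Section 8.1 item 9 has the same lymphoma clause and closing sentence, pointing to 10.6.2. It adds a Gilbert's limit: total at most 3 x ULN or direct at most 1.5 x ULN. Section 10.6.2 doses everyone on direct bilirubin: full dose up to 2 x ULN, 50% above 2 and up to 5 x ULN, withheld above 5 x ULN. Section 16.0 pools French and US data.

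**Chemistries.** AMC 8.1.12.2 and 8.2.6 and French 9.3 and 9.4 list total bilirubin only. On-treatment results need not be known before dosing unless clinically indicated.

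**The concern.** Two things looked wrong. First, one eligibility item sets a limit and then says not to exclude on a different test. Sites could admit or refuse the same patient with lymphoma-related liver involvement, a group for which 3.1.5 makes a specific allowance. Second, the AMC protocol exempts Gilbert's syndrome from the bilirubin limit at entry but has no line for it in the dosing table. A participant whose raised total bilirubin does not reflect impaired drug clearance could receive reduced doses of two curative-intent drugs, while the same patient enrolled in France would receive full doses within the same pooled analysis. AMC 5.2.1 asks for full AVD doses on schedule despite cytopenias, so an unneeded reduction runs against the protocol's own aim.

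**Working it through.** The plan gives no calculation on this point, so the rules are set side by side and applied to two cases.

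**Inputs from the documents**
- Doxorubicin 25 mg/m2 and vinblastine 6 mg/m2 on days 1 and 15 for 6 cycles: 2 x 6 = 12 doses.
- The entry limits and dose bands given above.
- 51 phase II participants, 20 expected in France (French Section 7.0): 51 - 20 = 31 under AMC rules.

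**Assumptions (not in the documents)**
- ULN ranges: total bilirubin 1.0 to 1.3 mg/dL, direct 0.2 to 0.4 mg/dL, AST 35 to 45 U/L.
- Table 5-C prints no units and is read in mg/dL and U/L.

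**Part (a): a lymphoma patient with total 2.5, direct 0.9, AST 100**
1. Total: 2.5 is at most 3.5, so it meets the antiretroviral limit.
2. AST: 100/45 = 2.2 to 100/35 = 2.9 x ULN, at most 3, so it meets the limit.
3. Direct: 0.9/0.4 = 2.25 to 0.9/0.2 = 4.5 x ULN. It is not normal, so the limit refuses the patient.
4. Reading the clause as the general limit changes nothing: 2.5/1.3 = 1.9 to 2.5/1.0 = 2.5 x ULN is not below 1.5.
5. Table 5-C: total and AST both fall in the 50% column. A dose is available, so the closing sentence keeps the patient.
6. ALT above 3 x ULN gives the same clash, because ALT is not in Table 5-C.
7. France: the antiretroviral limit refuses. Section 10.6.2 gives 50% for direct 2.25 to 4.5 x ULN, so the closing sentence keeps. If the clause is taken to mean the Gilbert's bullet, which comes just before it in the French text, a total of 1.9 to 2.5 x ULN is at most 3 and the patient is admitted.

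**Part (b): a Gilbert's participant not on atazanavir, direct normal, AST below 60**

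| Total (mg/dL) | AMC, bilirubin governs | AMC, AST governs | AMC, both must match | French 10.6.2 |
|---|---|---|---|---|
| 1.5 to 3 | 50% | 100% | no column | 100% |
| 3.1 to 3.5 | 25% | 100% | no column | 100% |

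Full totals are 25 x 12 = 300 mg/m2 doxorubicin and 6 x 12 = 72 mg/m2 vinblastine. If bilirubin governs and k doses are given at 50%, the totals are 300 - 12.5k and 72 - 3k:
- k = 1: 287.5 and 69;
- k = 6: 225 and 54;
- k = 12: 150 and 36.

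At 25% throughout: 300 x 0.25 = 75 and 72 x 0.25 = 18. If AST governs, the loss is 0.

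**How many.** The frequency of Gilbert's syndrome is not in the documents. Assuming 3% to 10%, 31 x 0.03 = 0.9 to 31 x 0.10 = 3.1, or about 1 to 3 AMC participants, fewer once atazanavir users are set aside.

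**Why not simply extend the atazanavir footnote.** It reads direct bilirubin on the total-bilirubin cut-offs. A direct value of 1.4 mg/dL is 1.4/0.4 = 3.5 to 1.4/0.2 = 7 x ULN, yet 1.4 is below 1.5 and would earn 100%. The French multiples give 50% or withhold; full dose ends at 2 x 0.2 = 0.4 to 2 x 0.4 = 0.8 mg/dL.

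**The case against.** **Entry.** A reader might infer that 3.1.9 and 5.2.5 refer to each other in a closed loop with no answer. The documents do not support that. The lymphoma sentence in 3.1.9 follows directly on the antiretroviral one, so its back-reference most naturally means that limit. The 3.5 mg/dL ceiling there matches the point at which Table 5-C stops giving a dose. The eligibility sentence in 5.2.5 follows the stenting sentence and may concern only those patients. The cyclophosphamide clause also suggests that the limit is meant to bind. Section 3.0 sends eligibility questions to the study chair and allows no exceptions. All of this narrows the conflict to patients with total at most 3.5 and raised direct bilirubin, or ALT above 3 x ULN. For them it does not remove it: the limit and the closing sentence still disagree, and referral helps only a site that notices.

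**Dose.** A reader might infer that AMC halves the dose in Gilbert's syndrome. The text supports only that it may. The header of Table 5-C is broken in the text available, so a rule for combining bilirubin with AST could have been lost. On the AST reading nothing is cut, and Gilbert's participants on atazanavir are already dosed on direct bilirubin. What stands is that the table has no Gilbert's line, although its footnote accepts that a raised total need not mean a lower dose.

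**Testing.** At baseline, direct bilirubin is already implied for the antiretroviral route, since every criterion must be documented. The gap is in the on-treatment chemistries.

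**Consequence.** The two protocols differ in other dose rules too, for example for febrile neutropenia (AMC 5.1.3 against French 10.6.2), so this difference is not distinctive.

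**Conclusion.** The point holds as a minor one, with moderate confidence. Part (a) is a real contradiction for a narrow group and needs a decision. The documents do not settle which way it should go: the limit and the cyclophosphamide route favour refusal, while the closing sentence and the allowance in 3.1.5 favour keeping these patients. Part (b) is an omission in the AMC dosing table. Depending on the reading, one affected participant loses nothing, half, or three quarters of the planned doxorubicin and vinblastine, while the French rule gives full dose.

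The worked cases rest on assumed ULNs and on reading Table 5-C in mg/dL and U/L; the count of about 1 to 3 rests on an assumed frequency. A reader might go on to infer that the pooled 2-year PFS estimate is biased. That does not follow: the number affected is unknown and probably small, and on one reading of the table there is no dose loss at all.

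**What to change.** 1. **Entry.** State in AMC 3.1.9 and French 8.1 item 9, in the same words, whether the limit or the dosing section decides entry for lymphoma-related elevation, and name the limit meant. If the limit binds, keep the cyclophosphamide cycle as the route to meeting it, and accept that some patients now kept would be refused. If the dosing section decides, entry would turn on total bilirubin in AMC and on direct bilirubin in France, which should be a deliberate choice.
2. **Dose.** In Table 5-C, dose Gilbert's participants on direct bilirubin with the French multiples: full dose up to 2 x ULN, 50% above 2 and up to 5 x ULN, withhold above 5 x ULN. Do not extend the atazanavir cut-offs to them.
3. **AST.** State how AST combines with bilirubin, for example that the lower of the two doses applies.
4. **Testing.** Measure direct bilirubin, with the result known before dosing, in every participant dosed on it: Gilbert's and atazanavir users in AMC, all participants in France.

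The cost is amendment wording, one added laboratory value with no new visits, and somewhat more doxorubicin and vinblastine for a few AMC participants. The protocols would still not be fully harmonised. Other AMC participants stay on total bilirubin, French dosing has no AST bands, and the French Gilbert's entry rule remains different.

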3.2 Exclusion Criteria

Patients who do not fulfill the criteria as listed in Section 3.1 above, are ineligible. Additionally, the presence of any of the following conditions will exclude a participant from study enrollment:

- 3.2.1 Patients with prior anthracycline therapy will be excluded.
- _____ 3.2.2 Female participants who are pregnant or breast-feeding. Confirmation that the

participant is not pregnant must be established by a negative serum b-human chorionic gonadotropin (b-hCG) or urine pregnancy test result obtained during screening. Pregnancy testing is not required for post-menopausal or surgically sterilized women.

- 3.2.3 Medical illness unrelated to HL, which in the opinion of the study physician will preclude administration of chemotherapy safely. This includes patients with uncontrolled infection (including opportunistic), chronic renal failure, myocardial infarction (MI) within the past 6 months, unstable angina, cardiac arrhythmias other than chronic atrial fibrillation, or second malignancy requiring active treatment.
- 3.2.4 Prior malignancy within 2 years before enrollment other than curatively treated cutaneous basal cell or squamous cell carcinoma, carcinoma in situ of the cervix, anal intraepithelial neoplasia, or cutaneous Kaposi's sarcoma (KS). Participants with prior malignancies must have completed all therapy at least 2 years before enrollment with no evidence of disease since therapy completion.
- _____ 3.2.5 Grade 2 or greater peripheral neuropathy.
- _____ 3.2.6 Evidence of PML identified on the pretreatment MRI.
- _____ 3.2.7 Central nervous system disease.
- _____ 3.2.8 Patients with history of JC Virus identified in the CSF or previous history of PML will be excluded from the study.
- 3.2.9 Cirrhosis secondary to any cause will be excluded.

3.3 Number of Participants to be Enrolled

- 3.3.1 Proposed Sample Size
 - For Phase I/II, this study will enroll a minimum of 6 participants.
 - For Phase I, this study will enroll a maximum of 18 participants.
 - For Phase II, this study will enroll a maximum of 51 participants.
 - If there are no DLTs observed in the Phase 1 portion of the study, and if 100% of all of the Phase 1 participants are treated identically to participants in Phase 2, accrual from the Phase 1 and 2 portions can be combined to complete the phase 2 portion of the study.
- 3.3.2 Accrual Rate
 - Approximately 2 participants per month.
- 3.3.3 Replacement of inevaluable participants

A participant who does not complete cycle 1 can be replaced if, based on a review of the available safety for that dose level, the principal investigator agrees that the events leading to participant withdrawal are unlikely to constitute a safety risk for further participant enrollment and dose escalation. This means that as long as participant safety is not compromised, a participant who withdraws from the study for administrative reasons prior to experiencing DLT during cycle 1 of therapy can be replaced by another participant to complete the number of participants evaluable per dose level required by the protocol. Similarly, as long as participant safety is not compromised, if an eligibility criterion or protocol violation occurs that substantially impairs evaluation of DLT during cycle 1, another participant can enter the cohort to complete the number of participants evaluable per dose level required by the protocol. Any replacement participant will be enrolled into the same dosing cohort as that for the participant who withdrew. Participants withdrawn because of brentuximab vedotin -related DLT may not be replaced.

3.4 Recruitment Plan

Participants seen in the inpatient or outpatient setting who meet eligibility criteria will be recruited to this study. Participation is voluntary. The participant will be made aware of his or her diagnosis and current nature of this treatment program. All participants will be required to sign a statement of informed consent that conforms to FDA regulations and Institutional Review Board (IRB) guidelines. IRB-approved advertisements to local periodicals, participant groups, or physicians may be used by each participating site.

3.5 Participant Enrollment Procedures

Sites must have this protocol approved by their Institutional Review Boards (IRB) and be registered for study participation with the AMC Operations and Data Management Center (ODMC) before they may enroll participants.

After it has been determined that the participant is eligible and an informed consent has been signed by the participant, the participant must be registered on-line via the AMC AdvantageEDCSM Internet Data Entry System (AdvantageEDC). Enrollment and data collection will occur via the AMC Internet Data Entry System.

The participating site will ensure a participant meets all eligibility criteria prior to completing the protocol-specific eligibility checklist in AdvantageEDC for enrollment. Participants will be enrolled on-line via AdvantageEDC no more than 1 week prior to the initiation of treatment (enrollment 1 day prior to or on the day of treatment is strongly encouraged). Once the eligibility checklist is submitted a system-generated confirmation email will be sent to the enroller upon successful completion of the participant enrollment. If the on-line system is inaccessible, the site should notify the AMC ODMC (via email at [contact] or via phone at [contact]) for further instructions.

4.0 TREATMENT PLAN

4.1 Phase I: AVD-Brentuximab Vedotin Therapy

AVD will be given in conjunction with the brentuximab vedotin on days 1 and 15 on a 28day cycle for 6 cycles. Standard, fixed-doses of AVD (doxorubicin 25 mg/m², vinblastine 6 mg/m², dacarbazine 375 mg/m²) will be administered intravenously. Brentuximab Vedotin will be administered *after* AVD (doxorubicin 25 mg/m², vinblastine 6 mg/m², dacarbazine 375 mg/m²). Brentuximab vedotin dosing will be determined by the phase I dose de-escalation schema with the starting dose of 1.2 mg/kg (See Table 4-A). For participants with weight exceeding 100kg, the dosage of Brentuximab vedotin will be calculated based on a weight of 100kg.

On the first cohort, three to six participants will begin at dose level 0. If > 1 dose-limiting toxicities (DLT) are encountered, 3 to 6 additional participants will be enrolled at the next lowest dose level. This will then be the MTD as long as no more than 1/6th of the participants experience DLT (1 participant of the 6 enrolled at that particular dose level). If more than one participant at any one dose level encounters a DLT, the dose will be deescalated for all subsequent participants (see Section 4.1.1 for DLT definition). Once a MTD has been confirmed, this will be the standard dose used in the phase II portion of the study. The phase I MTD was determined to be 1.2 mg/kg.

	Doxorubicin	Vinblastine Dacarbazine		Brentuximab Vedotin**
Dose Level	Day 1, 15 Of 28-day cycle			
0	25 mg/m ²	6 mg/m ²	375 mg/m ²	1.2 mg/kg**
-1	25 mg/m ²	6 mg/m ²	375 mg/m ²	0.9 mg/kg**
-2	25 mg/m ²	6 mg/m ²	375 mg/m ²	0.6 mg/kg**

Table 4-A: Phase 1 Dose Finding Schema for AVD-BV Regimen*

*See Section 4.4.1 for instructions on GCSF supportive treatment.

**For participants with weight exceeding 100kg, the dosage of Brentuximab Vedotin will be calculated based on a weight of 100kg.

4.1.1 Definition of Dose-Limiting Toxicity (DLT)

During cycle 1, any AE resulting in a dose delay in AVD-BV therapy of \geq 7 days is considered a DLT, which requires discontinuation of protocol-specified therapy and withdrawal from the study. Please refer to Table 5-A in Section 5.1 for specific guidelines. In subsequent cycles, the brentuximab vedotin dose may be withheld or reduced according to the guidelines provided in Section 5.1. If two sequential doses of AVD+BV or AVD alone are held due to unresolved toxicity, leading to a treatment delay of an additional 2 weeks (i.e., 4 weeks between doses), protocol treatment will be discontinued. Please see Section 4.6.1 for criteria for permanent treatment discontinuation.

